There is no standardized parameter to define an adequate adherence, it must be defined and outlined by the objectives of the research in particular. [62] The efficacy of ophthalmic steroids is based on two fundamental principles: 1) The specific type and location of the inflammation determines the appropriate route of administration and 2) The treatment should be instituted as soon as possible, and the dose should be high enough and administration frequent enough to suppress inflammatory activity. According to the therapeutic utility curve, to establish the limits of the therapeutic window, a dosage regimen is required in which 50% of the established doses are exceeded, in order to achieve a pharmacological effect. A therapeutic regimen below this value is expected a lack of efficacy. Therefore, an adherence of over 60% according to the weight of the bottle ensures that it remains within the limits of efficacy of the therapeutic window established in the protocol. [64] [65] [66] For the efficacy analysis, only subjects with a minimum adherence of 80% by means of the subject's daily tool and a minimum of 60% by the weight of the bottle will be considered. The variation in the percentage of the measurement method has been chosen empirically to counteract the sensitivity and specificity of the same. It is estimated that with a minimum adherence of 60% the intervention can exert its expected anti-inflammatory pharmacological action. [44]

6.3.3 Treatments and concomitant interventions allowed and prohibited before and during the study.

The subjects admitted correctly to the study, who meet the eligibility criteria, may continue with the systemic treatment of the underlying diseases. If during the development of the study they require the implementation of a new permitted medication, they may do so. All concomitant medications used must be duly reported in the notes of the clinical file and in the corresponding section.

Allowed medications:

- Ophthalmic:
- All permitted medications applied via ophthalmic during the study, must wait a minimum period of 10 minutes from the last application of the treatments under study or reference. The foregoing in order to avoid the interaction of the treatments in the tear film, based on the tear flow index and the physiological tear volume. [67]
 - Tetracaine 0.5%
 - Tropicamide 0.8% / Phenylephrine 5%
 - Any antibiotic
 - Beta-blockers
 - Alpha agonists
- Administered by a different route to ophthalmic:
 - Medications whose effect may be susceptible to modify any of the parameters of efficacy, safety or tolerability of this research protocol should notify their clinical monitor or scientific committee of the sponsor to judge the convenience of entry, continuation or elimination of the participant as appropriate.

Any medication allowed that is used, besides appearing in the clinical note, must be registered in the section of concomitant medications in the CRF.

- Prohibited medications:
- Any medication with ophthalmic application that is not on the list of allowed medications
- Systemic steroids
- Systemic NSAIDs
- Systemic immunomodulators
- Anticoagulants.

6.3.4 Treatment management.

The treatments will be provided by Sophia Laboratories, S.A. of C.V., for each research center. They will be labeled and reconciled. The handling of the treatment will be under the responsibility of the IP or a designated member of his team.

6.3.4.1 Delivery and reception.

The sponsor will be responsible for delivering the study treatments at the research center according to internal procedures. The delivery will be made in closed boxes by means of a courier service or directly by the sponsor's staff to the address of the research center according to the study plan.

The reception will be exclusively carried out by the research center team, including the IP. You must check the good condition of the primary packaging (box). In the event that it shows alterations or defects in its integrity that from its judgment could have damaged the content, it should report it to the sponsor. If the package does not show significant defects, it will proceed to open it.

Inside you must locate the acknowledgment document and the logger (data logger) of temperature and humidity. You should check that the registered temperature and humidity comply with the specifications for transport and shelter (see 6.3.4.2 Storage). Subsequently verify the content (treatments) with what is reported in the document. In case the document corresponds to the content, it will sign the receipt and send it to the sponsor. Otherwise, notify the sponsor.

In the study center, the personnel assigned by the IP will deliver the corresponding treatment to the inpatients. The center must register the medicine delivered.

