Creation date: July 2016

Clinical study of the efficacy of the ophthalmic emulsion PRO-145 for the management of inflammation and pain after phacoemulsification compared to prednisolone acetate 1%.

Protocol code: SOPH145-0716 / III

Protocol version: 2

Date of the version: 08/02/2018

Registration: Pending

Sponsor: Sophia Laboratories, S.A. of C.V.

Page left intentionally blank

1. Summary

Title of the study:	
Clinical study of the efficacy of the ophthalmic emulsion PRO-145 for the management of inflammation and pain, after phacoemulsification compared to prednisolone acetate 1%.	
Protocol code: SOPH145-0716/III	Creation date: 12/07/2016
Protocol version: 2	Date of the version: 08/02/2018
Therapeutic indication: Anti-inflammatory.	
Study period: 8 months	Development phase: III
Goals:	
To evaluate the efficacy of the ophthalmic emulsion PRO-145 in the treatment of inflammation and pain after phacoemulsification.	
Hypothesis:	
The use of the ophthalmic emulsion PRO-145 is effective in decreasing the inflammatory response evaluated by means of cellularity in the anterior chamber, after phacoemulsification.	
Methodology:	
Phase III clinical trial, double-blind, controlled, parallel group, multicentre, randomized.	
Number of patients:	
178 subjects divided into 2 groups (89 subjects per group), who will provide an eye for the evaluation of efficacy.	
Diagnosis and main inclusion criteria:	
Diagnosis: Postoperative phacoemulsification and foldable intraocular lens placement in a bag.	
Main criteria:	

 -Informed consent - Age \geq 18 years -Both genders - Postoperative cataract surgery by phacoemulsification 
 ○ o That they have met the criteria for phacoemulsification and a classification of the LOCS III cataract of NO \geq2 and NC \geq2 	
Test product, dose and route of administration:	

 • PRO-145. Difluprednate 0.05%. Prepared by Sophia Laboratories, S.A. of C.V., Zapopan, Jalisco, Mexico. - Dosage: 1 drop 4 times a day (every 4 hours) during the period of vigil in the operated eye, for 14 days. Dose reduction for 14 days at the discretion of the principal investigator. 	

- Route of administration: topical ophthalmic

Treatment duration:
 
28 days

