
Reference product, dose and route of administration:
 
1. Prednefrin® SF. Prednisolone Acetate 1%. Prepared by Allergan, S.A. of C.V.
 
- Dosage: 1 drop 4 times a day (every 4 hours) during the period of vigil in the operated eye, for 14 days. Dose reduction for 14 days at the discretion of the principal investigator.- Route of administration: topical ophthalmic

Evaluation criteria:
 
Effectiveness:
 
 • Primary 
 o Cellularity in the anterior chamber • Secondary 
 o Visual capacity (CV) o Central thickness of the retina or Clinical corneal edema or conjunctival hyperemia or Flare o Symptomatology 
 - Pain - Photophobia 
Tolerability:
 
 • Post-Stretching Ocular Symptomatology 
Security:
 
 • Visual capacity (CV) • Adverse events (EA) • Intraocular pressure (PIO)

Statistical methodology:
 
The result of the continuous quantitative variables will be presented in measures of central tendency: mean, standard deviation and ranges. The total size of the samples will consider an eye as a case for the evaluation of efficacy.
 
The normal distribution of the results will be obtained through the Kolmogorov-Smirnov and Shapiro-Wilks test. The statistical analysis of the continuous quantitative variables to find significant differences (p) will be in the inter-group analysis: t test for paired samples; for intra-group analysis: McNemar test. Evaluations of cellularity in the anterior chamber before the application of the intervention and in the final visit will be considered for the analysis. The level of difference to consider significance will be an alpha of 0.05 or less. The result of nominal and ordinal qualitative variables will be presented in frequencies, proportions and percentages. The statistical analysis to identify significant differences of the qualitative variables will be done creating 2x2 contingency tables and will be carried out as follows: Difference between groups: χ^2 test (Chi-square) of Pearson or Fisher's exact in expected values less than 5 ; for intra-group analysis: McNemar test

Page left intentionally blank

2. Content

1. SUMMARY	1
2. CONTENT	5
3. ABBREVIATION INDEX	9
4. ADMINISTRATIVE STRUCTURE OF THE STUDY	11
5. INTRODUCTION	13
5.1 THEORETICAL FRAMEWORK	13

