5.5.2 Specific objectives

- Evaluate the efficacy of PRO-145 through the elimination of anterior chamber cellularity (CCA) at the final visit.
- Evaluate the efficacy of prednisolone acetate 1% by means of the elimination of CCA in the final visit

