5.5.4 Hypothesis

H0: The use of the ophthalmic emulsion PRO-145 is not effective when decreasing the inflammatory response evaluated by means of cellularity in the anterior chamber, after phacoemulsification.

Ha: The use of the ophthalmic emulsion PRO-145 is effective in decreasing the inflammatory response evaluated by means of cellularity in the anterior chamber, after phacoemulsification.

5.6 Design and plan of the study.

Phase III clinical trial, parallel, controlled, randomized, double blind. Participants will be postsurgical phacoemulsification patients, who will be randomly assigned to 2 intervention groups with steroidal anti-inflammatory drugs. One group will receive the PRO-145 test formulation and the other group will be exposed to prednisolone acetate 1%.

[figure not shown]

Figure 2. Study design.

5.6.1 Discussion of the study design.

In clinical research it is common to propose trials with the objective of evaluating the efficacy of a product under investigation against a reference medicine or active control, in order to compare the new product under investigation from a clinical or statistical point of view to a drug commercially available

The clinical trial is the ideal model to evaluate the effectiveness of two interventions, it allows obtaining the highest quality evidence among different types of research. The characteristics of randomization and double blind, allow to avoid biases (selection, evaluation, etc.) that can not be avoided with other models. Being controlled and parallel groups allows distinguishing the effects of interventions in isolation.

The proposed clinical trial aims to evaluate the efficacy, safety and tolerability profile of a formulation of DFBA 0.05% and compare it against the safety, tolerability and efficacy profile of commercially available steroid administration, and widely used for its efficacy profile and known security.

6. Material and methods. Participants, interventions and variables.

6.1 Study Center.

The present study will be performed in ophthalmology offices duly equipped and registered for their proper functioning. According to the needs of the sponsor, these may be private or public, be attached to a hospital or clinic or be independent.

This is a multicentre study that is intended to be carried out in Guadalajara, Mexico City and Monterrey.

6.1.1 Organization of the center.

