8.3 Statistical methodology

8.3.1 Analysis of primary and secondary outcome variables

The statistical analysis will be carried out by personnel of Sophia Laboratories. The statistical program SPSS version 19 will be used.

The designated personnel will be blinded to the intervention groups. The coding will be done using consecutive numbers for each intervention group.

The data will be collected and sorted in an excel sheet. Later they will be exported to the platform of the SPSS program. The variables will be categorized according to their nature.

The results of the continuous quantitative variables will be presented in measures of central tendency: mean, standard deviation and ranges. See **Table 5 Variable measurement method**. The total size of the samples will consider an eye as a case for the evaluation of the efficacy.

The normal distribution of results will be obtained through the Kolmogorov-Smirnov and Shapiro-Wilks test, as applicable.

The statistical analysis of the continuous quantitative variables to find significant differences (p) will be the following:

. Inter-group analysis: t test for paired samples.

. Intra-group analysis: Mc Nemar test. Cellularity assessments in the anterior chamber will be considered for the analysis before the application of the intervention and in the final visit. The level of difference to consider significance will be of an alpha of 0.05 or less.

The result of nominal and ordinal qualitative variables will be presented in frequencies, proportions and percentages. See **Table 5 Method for measuring variables**

The statistical analysis to identify significant differences of the qualitative variables will be done by creating 2x2 contingency tables and will be done as follows:

- Difference between groups: χ^2 test (Chi-square) of Pearson or Fisher's exact in expected values less than 5.
- Intra-group analysis: Mc Nemar test.

The level of difference to consider significance will be an alpha of 0.05 or less.

For the reporting of adverse events all eyes of those participants who were randomly assigned to an intervention group will be considered. The results will be expressed in number of cases.

The final report of the results will be shown in tables or graphs, as appropriate.

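### A randomised two-arm trial has one-arm hypotheses, and no test, comparative claim, margin or confidence interval is named as deciding efficacy

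*Combined protocol and SAP*

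**What the plan says.** **Comparative intent.** The title sets PRO-145 against prednisolone acetate 1%. Section 5.6.1 says the trial will assess the difluprednate formulation and "compare it against the safety, tolerability and efficacy profile of commercially available steroid administration". Section 6.6.1 sizes the trial with a two-proportion formula.

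**Hypothesis and objectives.** Section 5.5.4 gives the alternative as "Ha: The use of the ophthalmic emulsion PRO-145 is effective in decreasing the inflammatory response evaluated by means of cellularity in the anterior chamber", and the null is its negation. The Summary repeats the alternative. Neither mentions the comparator. Section 5.5.2 has two specific objectives, one per arm: "Evaluate the efficacy of PRO-145 through the elimination of anterior chamber cellularity (CCA) at the final visit" and "Evaluate the efficacy of prednisolone acetate 1% by means of the elimination of CCA in the final visit".

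**Tests.** Table 5 classes anterior chamber cellularity as ordinal. For qualitative variables, section 8.3.1 uses 2x2 tables, with the "test (Chi-square) of Pearson or Fisher" exact test between groups and McNemar within groups, at alpha 0.05. The sentence that ties an analysis to the baseline and final cellularity readings stands elsewhere, in the block on continuous variables, directly after the within-group item: "Intra-group analysis: Mc Nemar test. Cellularity assessments in the anterior chamber will be considered for the analysis before the application of the intervention". The Summary has the same order: "for intra-group analysis: McNemar test. Evaluations of cellularity in the anterior chamber before the application of the intervention and in the final visit".

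**Timing.** Section 6.5 puts the baseline visit within 24 hours of surgery and the final visit at day 29. Both arms receive a topical steroid (section 6.3.1).

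**The concern.** The hypothesis is what the trial report will declare met or not met. Here it asks only whether PRO-145 reduces cellularity, and of the two tests that can apply to cellularity, the within-arm McNemar test fits that wording more closely. Nothing makes the conclusion depend on the between-arm result.

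Inflammation measured within a day of surgery may settle by day 29 with or without an effective drug. With a steroid in both arms and no untreated arm, a within-arm fall mixes drug effect with natural recovery. Randomisation protects only the between-arm contrast, so the plan permits an efficacy conclusion that the randomised comparison does not support.

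The plan is also silent on how to read a non-significant between-arm p-value. Superiority and non-inferiority treat the same data differently, and without a claim type, margin or interval a reader cannot tell what has been excluded.

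**Working it through.** **1. The passages side by side**

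| Element | Where | Arm or contrast |
|---|---|---|
| Title | Title page | PRO-145 vs prednisolone |
| Null and alternative | 5.5.4 (alternative also in Summary) | PRO-145 only |
| Specific objectives | 5.5.2 | One arm each |
| Design discussion | 5.6.1 | Comparison, no direction or margin |
| Sample size | 6.6.1 | Two proportions, no claim type or margin |
| Tests applicable to cellularity | 8.3.1, Table 5 | Chi-square/Fisher between; McNemar within; neither named primary |

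No section supplies a comparative hypothesis, claim type, margin or interval for the difference. The 95% in 6.6.1 is the type I error setting.

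**2. What a before/after test would require**

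Assumptions: cleared/not-cleared cut, exact two-sided McNemar. With b eyes cleared and c reversed, p = 2 × P(Bin(b + c, 0.5) ≤ c).
- b = 6, c = 0: p = 2 × 0.5^6 = 0.031.
- b = 5, c = 0: p = 2 × 0.5^5 = 0.0625.

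So with no reversals, six cleared eyes in an arm suffice. The documents give no clearance rate without drug effect and no reversal rate, so the chance of a spurious result cannot be estimated from them.

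**3. The plan's own sample size**

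Inputs from 6.6.1: 78.9% and 77.5%, z = 1.96 and 0.84, 74 per group, 20% for losses.
- Loss step: 2 × 74 = 148; 148 × 1.2 = 177.6, rounded to 178. This reproduces.
- Variance sum: 0.789 × 0.211 + 0.775 × 0.225 = 0.1665 + 0.1744 = 0.3409.
- Superiority: n = (1.96 + 0.84)² × 0.3409 / 0.014² ≈ 13,630 per group. The stated 74 does not reproduce. That is a separate finding and adds no weight here.

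**4. What 74 evaluable eyes per arm supports between arms**

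Assumption: the rates in 6.6.1 stand in for grade-0 rates. They describe reduction in the degree of cells, and section 5.3.1.4 describes their source as a study in children aged 0 to 3 years, whereas this trial enrols adults. Rates of 60% and 90% show the sensitivity.
- *Superiority at 78.9% vs 77.5%*, uncorrected chi-square, exact enumeration: probability of a significant result favouring PRO-145 = 0.039 (0.054 in either direction).
- *95% CI half-width at equal rates*, 1.96 × √(2p(1−p)/74): at 77.5%, 1.96 × √(0.34875/74) = 13.5 points (15.8 at 60%, 9.7 at 90%).
- *Margin giving 80% non-inferiority power*, one-sided 0.025, unpooled: at the stated rates, 2.8 × √(0.3409/74) − 0.014 = 0.190 − 0.014 = 17.6 points. At equal rates of 77.5%, 2.8 × √(0.34875/74) = 19.2 points (22.6 at 60%, 13.8 at 90%).
- *Probability that chi-square is non-significant when PRO-145 is truly worse*, control rate 77.5%: 72% for a 10-point deficit, 48% for 15, 25% for 20.

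The last line shows why a non-significant test cannot stand in for similarity.

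**The case against.** **A between-arm test is already specified.** This is right. Table 5 makes cellularity ordinal, so it belongs to the block of 8.3.1 that lists the between-group test first. The sentence on baseline and final cellularity sits among the continuous variables, where by Table 5 it does not belong, and may only fix the time points. A reader might infer that McNemar is the designated primary test, or that no between-arm test is planned. The documents support neither. What stands is that two tests at the same alpha are listed and neither is named as decisive.

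**Comparative intent is express.** The title and 5.6.1 do state it. Intent does not supply a claim type, margin or decision rule.

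**No similarity claim is made.** Also correct. A reader might infer that the sponsor means to present a non-significant result as equivalence. No text says so. The error rates in step 4 matter only if it is read that way.

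**The before/after risk cannot be quantified.** This stands. A percentage for how often McNemar would succeed without drug effect depends on clearance and reversal rates that the documents do not give. Only the six-to-nil illustration is free of assumed rates.

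**A between-arm result does not by itself prove drug effect either.** This stands too. Non-inferiority to prednisolone is informative only with evidence that prednisolone works in this setting, so that evidence must underlie any margin.

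**Conclusion.** The point holds and should be corrected before any comparative analysis. The hypothesis concerns PRO-145 alone, each specific objective concerns one arm, and 8.3.1 names no decisive test, comparative hypothesis, claim type, margin or interval. A before/after fall could therefore be reported as meeting the hypothesis in a trial whose design cannot attribute that fall to the drug. This rests on the wording and needs no assumed rate.

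At 74 evaluable eyes per arm, and treating the rates in 6.6.1 as grade-0 rates, power for superiority of PRO-145 is about 4%, and the 95% interval is about ±13.5 points. Non-inferiority reaches 80% power only at margins of about 17.6 points (stated rates) or 19.2 points (equal rates of 77.5%). These figures describe the design and do not justify a margin.

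The unranked analysis populations (6.3.2, 8.3.3) and the sample size that does not follow from its stated rates are separate matters. They do not add to the severity of this one.

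**What to change.** - In 5.5.2, 5.5.4, the Summary and 8.3.1, make the primary analysis the between-arm difference in the proportion with cellularity grade 0 at the final visit, with a two-sided 95% confidence interval.
- Make the within-arm McNemar tests descriptive.
- State that a non-significant between-arm test is not evidence of similarity.
- State the claim type and, for non-inferiority, a margin justified by evidence of the comparator's effect in this setting and compared with the lower confidence limit.
- Fix both before any partial, sponsor-requested or group-coded comparative analysis. Before unblinding is too late: the analysts work on coded groups (8.3.1), and analyses during the study are foreseen (7.4, 8.3.2, 9.2).
- If no claim type or margin can be justified, report the difference and interval as an estimate, with no superiority or similarity claim.
- State what 74 evaluable eyes per arm supports, using the figures above.

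**Cost.** A protocol amendment, with ethics and research committee approval and then regulatory authorisation (10.2). Reporting the difference with its interval needs no extra patients. The claim becomes harder to win than a before/after test, and the planned size is not adequate for superiority at the stated rates or for a tight margin.

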 - Any disease or condition that requires the use of steroids other than topical ophthalmic application.
 - Subjects with a single eye.
 - Any condition or disease that at the discretion of the IP does not make the subject suitable for the study.
 - Known hypersensitivity to the components of the products under investigation.

6.2.3 Elimination criteria.

- Decision of the subject. The subject can decide unilaterally to withdraw from the study at any time, should inform the IP.
- Pregnancy.
- Presence of a serious adverse event (EAS).
- Investigator's decision:
 - o Due to the presence of an AD that at the discretion of the IP threatens the health of the subject and requires the prescription of a medicine not authorized in the protocol
- Any deviation to the protocol that affects the safety of the subject.

6.2.4 Identification of the subject.

The patients of the study will be identified by a number and the initials of their name.

The initials of the study subject will be obtained by starting with the first letter of the name, followed by the first letter of the first surname and the first of the second, obtaining maximum three letters, in case the person has two names or a compound surname will always be used the first letter of the first name or last name composed.

Example:

1. Adolfo Daniel Mercado Carrizales

to. Initials: AMC

2. Juan De la Torre Orozco

to. Initials: JDO

[figure not shown]
3. Luis Carlos Pérez-Gómez Ramírez

to. Initials LPR

In the counting stage, the participant number will be assigned consecutively, using 3 consecutive digits. Once the subject has been selected, he will be assigned a number with which he will be identified throughout the study. Said code will be composed of eight numbers in the following order from left to right:

- three digits of the molecule under study according to the denomination by the sponsor.
- two digits corresponding to the research center number
- three digits of the number consecutive to their inclusion assigned in the research center.

Example:

6.3 Intervention .

6.3.1 Managed treatments.

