Medication counting is another way to measure adherence. Classically referred to as "pills counting", in ophthalmology it is translated to the weight of the bottle. This is a simple, economical and non-invasive method. The main disadvantages of this method are: 1. The application of the medication can not be confirmed (it could have been intentionally thrown or instilled outside the eye) and 2. It depends on the subject bringing the medication back. [62] [63]

The approach with multiple procedures for measuring adhesion is recommended. Because there is no ideal adhesion measurement, it is appropriate to use more than one method when trying to achieve results that resemble reality. Selecting two or more methods allows their strengths and weaknesses to be compensated, in order to more reliably capture adherence levels. [61]

- The evaluation of the adherence by means of the diary of the subject will be carried out in the following way:

$$Ad = (A_r)100/A_i$$

Where:

Ad = Adherence

Ar = Applications registered in the first 14 days of treatment.

Ai = Applications indicated for the intervention in the first 14 days of treatment.

At the sponsor's facilities, the bottles will be weighed at the beginning and at the end of the study. The adhesion will be calculated considering: the weight of the empty bottle, the weight of the drop, the weight of the bottle with the content, the calculation of the total of drops to be applied during the entire time of intervention and the total weight of the drops applied. The following simplified formula will be used:

$$Ad = \frac{(P_i - P_f)100}{P_T}$$

Where:

Ad = adhesion

IP = weight of the bottle delivered to the subject at the start

Pf = weight of the bottle returned by the subject

PT = weight of the posology indicated for the intervention.

$$P_T = (P_g)G$$

Where:

P_g = weight of the drop of the intervention, determined by the department of research and development

G = number of drops indicated for the intervention

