- Delivery of the subject's diary: see 6.5.2.1 Baseline visit, this visit is made upon delivery of the diary of the subject delivered at the baseline visit.
- Indication to change to dose reduction scheme: It refers to the indication of the IP to initiate the dose reduction scheme on day 15 of the study, and to last the remaining 14 days of the intervention. The IP will determine, according to the patient's clinical condition, the scheme to follow. It will record in the clinical note and in the CRF, the outline and total number of applications indicated. Example: 1 drop 3 times a day for 5 days; followed by 1 drop 2 times a day for 5 days; finish with 1 drop a day for 4 days; and suspend (Total number of applications indicated: 29). In case visit 2 is made on day 15 that same day, the scheme must be readjusted; if the visit is made on day 16 the scheme will be adjusted from that day and for the remaining 12 days.

6.5.2.4 Final Visit.

- Pregnancy test: see 6.5.2.1 Baseline visit.
- Ophthalmological examination: see 6.5.2.1 Baseline visit.
- Biomicroscopy: see 6.4.3.1 Biomicroscopy
- Visual capacity: see 6.4.3.2 Visual capacity
- History of symptomatology: see 6.4.3.4 History of symptomatology
- OCT: see 6.4.3.5 Optical coherence tomography
- Tonometry: see 6.4.3.6 Tonometry
- Evaluation of concomitant medications: see 6.5.2.1 Baseline visit.
- Evaluation of adverse events: see 6.4.3.3 Evaluation of adverse events
- Continuity assessment: see 6.5.2.2 Visit 1
- Adherence evaluation: see 6.5.2.2 Visit 1
- Return of the medication: refers to the delivery, by the subject, of the excess medication to the research center.

6.5.2.5 Security call:

- Evaluation of adverse events: see 6.4.3.3 Evaluation of adverse events.

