8.1.1 Strategies to complete the follow-up

- You will be informed in a clear way the importance of the study and the benefits that the population will obtain from the results of the study.

- Transportation assistance will be provided in order for the participant to attend their visits.
- A printed calendar will be provided with the objective of reminding the participant of their appointments and the activities that will be carried out, in addition to the estimated duration of the same.
- In case the participant does not attend his / her appointment, the research center must make a call to know the reason and try to arrange a new appointment within the established window period or an unscheduled appointment.
- In case it is not possible to make an appointment, it will be asked about the presence of adverse events and the reason for leaving the study, as minimum data.

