8.3.3 Population analysis and management of missing data

The effectiveness analysis will consider those cases in which the measurements of the baseline and final visit are met. Those subjects who do not comply with any of these measurements will not be integrated into the final database to evaluate the effectiveness. Nevertheless, an intention to treat analysis (ITT) will be carried out.

The safety assessment will include in the analysis all those subjects (considering one eye or both) who have been exposed at least once to any of the interventions regardless of the visit in which they were eliminated from the study.

9. Methods Monitoring

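### Section 6.2.3 offers only elimination from the study, so an eye that fails and needs an unauthorised anti-inflammatory can leave the main efficacy analysis through a missing final grade

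*Combined protocol and SAP*

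**What the plan says.** - **Leaving the study (6.2.3).** Every entry is a reason for elimination. The investigator may eliminate a subject for an event (abbreviated AD, most naturally an adverse event) that "threatens the health of the subject and requires the prescription of a medicine not authorized in the protocol". Stopping drug and continuing visits is not listed.
- **Lack of response (9.3.1.1).** It is to be recorded as an adverse reaction.
- **Rescue (6.3.3).** The permitted ophthalmic list contains no steroid or NSAID, and ophthalmic products off the list are prohibited.
- **Data on leaving (6.5.1, 8.1.1).** The schedule has no exit visit. After a missed appointment the centre first calls and tries to arrange another. Only if that fails does the minimum apply: "it will be asked about the presence of adverse events and the reason for leaving the study, as minimum data".
- **Effectiveness set (8.3.3).** Baseline and final-visit measurements are both needed: "Those subjects who do not comply with any of these measurements will not be integrated into the final database to evaluate the effectiveness". The section adds that "an intention to treat analysis (ITT) will be carried out", with no rule for missing or rescued eyes. Safety, by contrast, keeps exposed subjects "regardless of the visit in which they were eliminated from the study".
- **Adherence filter (6.3.2).** Entry to the efficacy analysis requires "a minimum adherence of 80% by means of the subject's daily tool and a minimum of 60% by the weight of the bottle". The diary denominator is "Applications indicated for the intervention in the first 14 days of treatment".
- **Objective (5.5.2).** Elimination of anterior chamber cells at the final visit, stated separately for each arm.

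**The concern.** An eye taken off study drug because inflammation is not controlled, and given another anti-inflammatory, is a known failure on the primary objective. If leaving drug also means leaving the study, that eye has no final-visit grade and drops out of the denominator of the effectiveness analysis. The remaining eyes are selected for having done well enough to stay.

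Because the objective is stated arm by arm, removing known failures overstates each arm's clearance rate even when the losses are balanced. If they are unbalanced, the comparison shifts in favour of the arm with more of them. The ITT analysis is where one would look for protection, but nothing says how such an eye enters it.

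**Working it through.** **1. The route.** A poor response is recorded as an adverse reaction (9.3.1.1). The investigator judges that it threatens health and needs a drug that 6.3.3 does not permit. Section 6.2.3 then allows elimination. No exit visit is scheduled, so no final-visit grade is assured, and 8.3.3 removes the eye. Each step is possible under the text; none is automatic. A failure found at visit 1 or 2 would normally have a cell grade from that visit, because biomicroscopy is scheduled there (6.5.1), but no rule carries that grade into either analysis.

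**2. Effect on one arm's rate.** The plan gives no rescue rate, so this is an illustration.
- Eyes per arm: n = 89 (6.6).
- Cleared: 0.775 × 89 = 69, leaving 20 failures. The 77.5% is the prednisolone rate in 6.6.1. It is described there as a reduction in cell grade, so using it for clearance is an assumption.
- True rate 69/89 = 77.5%. With k failures removed, the observed rate is 69/(89 − k).

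| k removed | Observed rate | Overstatement |
|---|---|---|
| 1 | 69/88 = 78.4% | 0.9 points |
| 2 | 69/87 = 79.3% | 1.8 points |
| 3 | 69/86 = 80.2% | 2.7 points |
| 6 | 69/83 = 83.1% | 5.6 points |

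**3. Effect on the comparison, equal true rates.** The standard error is √[p₁(1−p₁)/n₁ + p₂(1−p₂)/n₂].
- 2 v 2 removed: difference 0.0 points, standard error 6.1.
- 1 v 3 removed: 80.2 − 78.4 = 1.8 points, standard error 6.1.
- 2 v 6 removed (10% v 30% of failures): 83.1 − 79.3 = 3.8 points, standard error 6.0.

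**4. Keeping the eyes is not enough.** If two rescued eyes stay and a post-rescue grade 0 counts as success, the rate is (69 + 2)/89 = 79.8%, or 2.2 points high. That is worse than dropping them (1.8 points), so a failure rule is needed as well.

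**5. The adherence filter.** Four drops a day for 14 days is 56 applications. The example taper in 6.5.2.3 is 3×5 + 2×5 + 1×4 = 29, which matches "Total number of applications indicated: 29", so the full course is 56 + 29 = 85. The thresholds are 0.80 × 56 = 44.8 by diary and 0.60 × 85 = 51 by weight. Section 6.3.2 does not say which denominator applies when the investigator stops the drug.

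| Stopped after | Full schedule, diary | Full schedule, weight | Indicated to date |
|---|---|---|---|
| day 7 | 28/56 = 50% | 28/85 = 33% | 28/28 = 100% |
| day 9 | 36/56 = 64% | 36/85 = 42% | 36/36 = 100% |
| day 14 | 56/56 = 100% | 56/85 = 66% | 56/56 = 100% |

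Under the full schedule, an eye stopped by the end of the visit 1 window (day 9) fails the filter. Under applications indicated to date, it passes. At day 14 it passes on either reading, and only the missing final grade matters.

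**The case against.** The strongest reply is that the route is narrow and the protocol leaves room to avoid it. The criterion needs both a threat to health and an unauthorised medicine, at the investigator's discretion. Residual cells at the final visit, the ordinary failure, do not trigger it. Both arms receive an active steroid, and the taper follows clinical condition (6.5.2.3). Section 9.3.1.3 leaves withdrawal or permanence to the investigator, 9.3.1.1 allows for maintained or restarted drug, and 9.3.1.2 has adverse events followed to their end. For non-ophthalmic medicines, 6.3.3 lets the sponsor judge continuation. Using prohibited medication is a major deviation (10.5) but does not by itself eliminate a subject.

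All of this stands, and it limits how often the problem can arise. None of it requires a cell grade at the final visit once drug has stopped, or says how such an eye counts.

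A reader might infer that the adherence filter is a second, independent way of losing these eyes. The documents do not support that. Section 6.3.2 speaks of applications indicated, which can be read as those indicated up to the stop, and then nobody is removed. An eye eliminated early would usually lack a final grade anyway, so the filter is largely redundant. It matters mainly once such eyes are kept in follow-up.

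A reader might also infer that an eliminated subject leaves no efficacy data. That goes too far, because grades from visits already attended exist and 8.1.1 first seeks a new appointment.

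Finally, counting rescue as failure in every set is a choice. Applying the rule to ITT alone, with the adherent completers as support, is also defensible, but ITT would then have to be named the main analysis.

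**Conclusion.** The point holds in limited form. Following 6.2.3 and 8.3.3 as written can remove known failures from the effectiveness denominator, and the one-line ITT commitment does not repair this. Each arm's clearance rate can be overstated by about 1 to 2 points for one or two eyes, assuming 89 per arm and 77.5% clearance. The comparison is biased only if such losses differ by arm; an assumed 2 v 6 split gives 3.8 points, below one standard error.

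A reader might infer that this could decide the trial. Removing failures equal to 10% of randomised eyes (about 9 of 20 failures) from one arm and none from the other would give 0.775/0.90 = 86.1% against 77.5%, a false gap of 8.6 points. The documents give no rescue rate and no reason to expect such an imbalance. This is a cheap improvement worth making, not a flaw that settles the result on its own.

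**What to change.** 1. **6.2.3:** separate stopping study drug from leaving the study. Unless consent is withdrawn, keep the remaining scheduled visits; if the subject cannot return, take the final-visit measurements on the day of leaving.
2. **8.3.3:** count any subject rescued or eliminated for inadequate control of inflammation as not having eliminated cells, whatever the post-rescue grade, in both the ITT analysis and the main effectiveness analysis.
3. **6.3.2 (safeguard):** state that adherence is not a ground for excluding a subject whom the investigator stopped for lack of response. This removes the dependence on which denominator is meant.

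The cost is protocol and consent wording, a few already-scheduled visits off drug, and slightly lower reported clearance rates. Rescue therapy and its dates are already recorded under 9.3.1.1, so no new form is needed.
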